5.1. SUBJECT DISPOSITION, DEMOGRAPHIC AND BASELINE CHARACTERISTICS

Subject disposition will be presented for all subjects. The number of subjects who completed the study and discontinued from the study will be provided. The reasons for early discontinuation also will be presented. Additionally, the number of days on study will be summarized.

A CONSORT diagram will be produced showing the number of subjects screened, number of screening failures, number of subjects by age group, number in each of the study populations, and number who complete the study.

Demographic data and baseline characteristics including age, gender, race, ethnicity, Baseline Composite Symptom Score, baseline viral titer status, the number subjects who had hypothermia ($< 35^{\circ}\text{C}/95^{\circ}\text{F}$), normal temperature (35 to $< 37.4^{\circ}\text{C} / 95$ to $< 99.4^{\circ}\text{F}$), or fever ($\geq 37.4^{\circ}\text{C}/99.4^{\circ}\text{F}$) at baseline, height, weight, and body mass index (BMI) will be summarized using descriptive statistics for the ITT, ITTI, safety, and exposure-response populations.

Enrollment by site, eligibility, treatment status, and screening RAT and PCR test results will be summarized by age group and overall.

This information will be reviewed for baseline differences, but no statistical testing will be performed.

Subject diary completion will be summarized including the days of diary completion.

5.2. EFFECTIVENESS ANALYSIS

5.2.1. Effectiveness Endpoints

The effectiveness endpoints include:

- Time to resolution of fever
- Time to alleviation of clinical symptoms of influenza
- Change (reduction) in influenza virus titer by \log_{10} TCID₅₀/mL
- Change (reduction) in influenza virus titer by RT-PCR results
- Changes in viral shedding measured by quantitative viral titer assay (TCID₅₀) and/or quantitative PCR.
- Change in influenza virus susceptibility to neuraminidase inhibitors
- Incidence of influenza-related complications as determined by investigator
- Incidence of hospitalization admission post treatment
- Usage of antipyretic medication
- Change in daily activities per the visual analog scale
- Time to resumption of usual daily activities per the visual analog scale

5.2.2. Effectiveness Analyses

A subject's oral temperature taken by subjects and recorded in the diary by subjects/caregivers will be summarized by age group and overall by study visit. A subject has Resolution of Fever if he/she has an oral temperature $< 37.4^{\circ}\text{C}/99.4^{\circ}\text{F}$ oral and no antipyretic medications have been taken for at least 12 hours. The time to resolution of fever will be estimated for each age group and overall using the Kaplan-Meier method with temperature and symptom relief medication information obtained from the subject diary data. Subjects who do not have resolution of fever will be censored at the time of their last non-missing post-baseline temperature assessment.

Alleviation of symptoms will be determined by assessment of symptoms as reported on each Subject Diary. The time to alleviation of symptoms, defined as the time from initiation of study drug until the start of the 21.5 hour period (24 hours less 10%) where all symptoms of influenza are recorded as none or mild, will be estimated overall and for each age group using the Kaplan-Meier method. Subjects who do not experience alleviation of symptoms will be censored at the date of their last non-missing post-baseline assessment.

Change from baseline in \log_{10} TCID₅₀/mL through Day 3, Day 7, and Day 14 will be presented by age group and overall for subjects with positive viral titers at baseline (\log_{10} TCID₅₀/mL > 0.5). A box plot and a histogram of the TCID₅₀/mL values will be presented by visit and age group. In addition, the median change from baseline in TCID₅₀/mL will be presented by visit and age group.

The number and percent of subjects with positive viral titers at baseline (\log_{10} TCID₅₀/mL > 0.5) that shed virus at each visit will be presented by age group and overall.

The RT-PCR results at each visit will be presented by age group and overall for subjects with positive RT-PCR results at baseline.

Change from baseline to last positive value of influenza virus susceptibility to neuraminidase inhibitors will be assessed using virology laboratory tests. Virology laboratory tests will include phenotypic characterizations of influenza virus recovered (hemagglutinin and neuraminidase) and viral susceptibility to zanamivir, oseltamivir, and peramivir, as well as genotyping of virus isolates. These analyses will be presented overall and by age group and viral subtype.

The development of any post treatment genotypic changes in neuraminidase and hemagglutinin will be assessed by comparison of sequences from baseline and last positive post-treatment virus samples. These analyses will be presented overall and by age group and viral subtype.

The number and percentage of subjects experiencing influenza related complications will be summarized by age group and overall by complication MedDRA version 18.0 preferred term.

The number and percentage of subjects who are hospitalized due to any TEAE and due to any TEAE related to study drug after initiation of treatment will be summarized by age group and overall.

The number of doses of antipyretic medications, as recorded in the subject diary, taken throughout the study and by study day will be summarized by age group and overall.

The change in daily activities will be summarized each day by age group and overall. The ability to perform usual activities is defined as a subject rating of 10 (able to perform all usual activities fully) on the visual analog scale the subject uses to rate his or her current ability to perform usual activities compared with normal ability. The time to return to usual activities will be estimated for each age group and overall using the Kaplan-Meier method. Subjects who do not return to normal activities will be censored at the time of their last non-missing post-baseline assessment.

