**Table 1. BCX1812-306: Schedule of Assessments**

Assessments	Screening 	Baseline  (Pre-dose)	Day 1 Treatment Day 	Day 3	Day 7 (+ 2 days)	Day 14 (+ 3 days) / End of Study	Early Withdrawal
Informed Consent	X						
Inclusion/Exclusion Criteria	X						
Medical History/Physical Exam	X			X 	X 		
Vital Signs 	X			X	X	X	X
Body Temperature 	X	X	X	X	X	X	X
Clinical Chemistries and Hematology 		X			X		X
Urinalysis 		X			X		X
Pregnancy Test (Urine or Serum)	X					X	X
Assessment of influenza symptoms 	X		X	X	X	X	X
Ability to Perform Usual Daily Activities 		X		X	X	X	X
Influenza Related Complications (IRC) 	X			X 	X	X	X
Concomitant Medications Review	X		X	X	X	X	X
Subject Diary Review			X	X	X	X	X
Pharmacokinetic (PK) Sampling			X				
Serum sample for influenza antibody analysis 		X		X	X		X
Swabs for Virology Analysis		X		X	X		X
Rapid antigen test (RAT) or FDA- approved PCR test for influenza A and B on nasal specimen	X						

Assessments	Screening	Baseline (Pre-dose)	Day 1 Treatment Day	Day 3	Day 7 (+ 2 days)	Day 14 (+ 3 days) / End of Study	Early Withdrawal
Study Drug Administration			X				
Adverse Events 	X	X	X	X	X	X	X

- 1 It is expected that the date of Screening, Baseline, and Day 1 (date of study drug administration) will be the same. Day 1 consists of pre and post-dose assessments.
- 2 Vital sign measures will include blood pressure, pulse rate, and respiration rate. Vital signs will be recorded once during Screening, and vital signs will be taken once on remaining study visit days.
- 3 The investigator will record oral body temperature at Screening. Thereafter, the subject or care giver will record oral body temperature approximately every 12 hours in the Subject Diary until temperature normalizes for 48 hours (i.e. temperature without antipyretic is < 37.4°C/ 99.4°F orally for 4 measurements).
- 4 Clinical laboratory assessments performed at Screening are for the purpose of establishing a baseline. Subjects may be enrolled and begin treatment with study drug prior to receiving results. These labs may be done at any visit if necessary for patient management or adverse event monitoring purposes.

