- Assessment of the presence and severity of each of 7 symptoms of influenza on a 4-point severity scale (0, absent; 1, mild; 2, moderate; 3, severe) at Screening, then twice daily through Day 13, and prior to the subject's clinic visit on Day 14 or until each symptom is 0 or 1 for 48 hours. Symptoms will be reviewed at each clinic visit.
- Temperature measurements (oral) will be taken with an electronic thermometer provided by the Sponsor, approximately every 12 hours until temperature normalizes for 48 hours (i.e. temperature without antipyretic is  $< 37.4^{\circ}\text{C} / 99.4^{\circ}\text{F}$  orally for 4 measurements). With the exception of the Screening/ Baseline measurement, all temperature measurements will be

obtained at least 4 hours after, or immediately before, administration of oral acetaminophen or other antipyretic medications, if taken.

- The type, date, and time of medications used for the symptomatic treatment of influenza-related symptoms.
- Assessment of the subject's ability to perform usual activities using a 0 to 10 visual analogue scale once daily through Day 14, where 0 = Unable to perform usual activities at all, and 10 = Able to perform all usual activities fully.

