##### **10.1.2.2. Day 1/Post-dose**

The following procedures/evaluations will be performed post-dose on Day 1:

- Collect up to 3 plasma samples, where possible, during the following time periods, beginning from the end of dosing until release from the site. For each plasma sample the calendar date and 24-hour clock time of sample collection will be recorded:
  - One time point immediately following completion of the infusion
  - One time point from 30 minutes to 1 hour post-infusion
  - One time point from 1 hour to 3 hours post-infusion
- Train the subject/caregiver on the recording of the following in the subject diary:
  - Subject's body temperature, obtained at approximately 12-hour intervals each day until the temperature normalizes for 48 hours (and 4 hours from last antipyretic medication administration or immediately prior to administration).

- Instruct the subject to assess his/her time lost from work, if applicable, and the recording of the subject's ability to perform usual daily activities using a 0 to 10 visual analogue scale.
- Assessment of signs and symptoms of influenza twice daily beginning on Day 1 (see Section [10.2.2](#)).
- Review and record concomitant medications
- Obtain and record body temperature
- Review and record AEs

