#### **10.2.1. Body Temperature**

The Investigator will record oral body temperature at Screening. The baseline temperature will be recorded at the Day 1 visit prior to dosing, regardless of whether the subject had recently taken an antipyretic. Thereafter, the subject or caregiver will record oral body temperatures approximately every 12 hours through Day 14 in the subject diary. Subjects or caregivers will measure their oral temperature with an electronic thermometer (provided by the Sponsor for the study). With the exception of the

baseline measurement, subjects will be instructed to take all temperature measurements at least 4 hours after, or immediately before, administration of oral acetaminophen or other antipyretic medications. The times of each temperature determination will be recorded in the Subject Diary.

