9. PROPOSED TABLES, LISTINGS, AND FIGURES FOR FINAL ANALYSIS

Output Number	Output Title
Table 14.1.1	Subject Follow-Up and Termination from Study: Intent-to-Treat Population
Table 14.1.2.1	Eligibility and Treatment Status: Intent-to-Treat Population
Figure 14.1.2.2	BCX1812-306 Study Population Disposition: Intent-to-Treat Population
Table 14.1.3	Populations for Analysis: Intent-to-Treat Population
Table 14.1.4.1	Demographics and Baseline Characteristics: Intent-to-Treat Population
Table 14.1.4.2	Demographics and Baseline Characteristics: Intent-to-Treat Infected Population
Table 14.1.4.3	Demographics and Baseline Characteristics: Safety Population
Table 14.1.4.4	Demographics and Baseline Characteristics: Exposure-Response Population
Table 14.1.5	Summary of Subject Diary Completion: Intent-to-Treat-Infected Population
Table 14.2.1.1	Summary of Oral Temperature Diary Assessments (°C): Intent-to-Treat Infected Population
Table 14.2.1.2	Time to Resolution of Fever: Intent-to-Treat Infected Population
Table 14.2.1.2.X	Time to Resolution of Fever: Viral Subtype: Intent-to-Treat Infected Population
Figure 14.2.1.3	Time to Resolution of Fever (Kaplan-Meier Plot): ITTI Population
Figure 14.2.1.4	Median (95% CI) Time to Resolution of Fever: ITTI Population
Figure 14.2.1.5	Box Plots of Time to Resolution of Fever: ITTI Population
Table 14.2.2.1	Time to Alleviation of Symptoms: Intent-to-Treat Infected Population

Output Number	Output Title
Table 14.2.2.1.X	Time to Alleviation of Symptoms: Viral Subtype: Intent-to-Treat Infected Population
Figure 14.2.2.2	Time to Alleviation of Symptoms (Kaplan-Meier Plot): ITTI Population
Figure 14.2.2.3	Median (95% CI) Time to Alleviation of Symptoms: ITTI Population
Figure 14.2.2.4	Box Plots of Time to Alleviation of Symptoms: ITTI Population
Table 14.2.3.1	Summary of Changes \log_{10} Tissue Culture Infective Dose ₅₀ (TCID ₅₀ /mL) by Study Visit: Subjects with Positive Baseline Titers; Intent-to-Treat Infected Population
Table 14.2.3.1.X	Summary of Changes \log_{10} Tissue Culture Infective Dose ₅₀ (TCID ₅₀ /mL) by Study Visit: Subjects with Positive Baseline Titers: Viral Subtype: Intent-to-Treat Infected Population
Figure 14.2.3.2	Box Plots of Viral Titers (TCID ₅₀ /mL) by Study Visit; Subjects with Positive Baseline Titers: Intent-to-Treat Infected Population
Figure 14.2.3.3	Histograms of Viral Titers (TCID ₅₀ /mL) by Study Visit; Subjects with Positive Baseline Titers: Intent-to-Treat Infected Population

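### If diary temperature recording stopped after 48 normal hours, the Day 7 and Day 14 rows of the by-visit diary table describe a subset selected by outcome; Protocol 10.2.1 contradicts that stop rule

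*SAP*

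**What the plan says.** **The analysis.** SAP 5.2.2 states that diary oral temperature "recorded in the diary by subjects/caregivers will be summarized by age group and overall by study visit". The matching output is Table 14.2.1.1, titled "Summary of Oral Temperature Diary Assessments (°C): Intent-to-Treat Infected Population".

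**The recording rule, version A (stop).** Protocol 10.1 has temperature taken "approximately every 12 hours until temperature normalizes for 48 hours". Footnote 3 of Protocol Table 1 says "approximately every 12 hours in the Subject Diary until temperature normalizes for 48 hours". The Day 1 diary training in Protocol 10.1.2.2 describes readings "obtained at approximately 12-hour intervals each day until the temperature normalizes for 48 hours". The protocol synopsis and SAP 1.1 and 1.2 repeat the same stop.

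**The recording rule, version B (no stop).** Protocol 10.2.1, the section devoted to body temperature, says: "Thereafter, the subject or caregiver will record oral body temperatures approximately every 12 hours through Day 14 in the subject diary".

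**Missing readings.** SAP 3.3.4 imputes missing diary completion times and sets censoring rules for time-to-event endpoints, then rules out other imputation. No temperature value is filled in. SAP 8 bases continuous summaries on the non-missing observations.

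**Clinic readings.** Protocol 10.1.2.3 to 10.1.2.5 also schedule oral temperature at the Day 3, 7 and 14 visits. SAP 5.2.2 names only the diary as the source for the by-visit summary, and vital signs as defined in the schedule of assessments do not include temperature.

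**The concern.** Under version A, whether a subject has a diary reading at a late visit depends on the quantity being summarised. Those who recover early leave the table as instructed, and those who have not recovered stay in it. A mean over the non-missing values then describes the slow end of the cohort while it is labelled as the infected population at that visit. The trial has one arm, so no comparator would show the artefact.

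At stake is the reading of one supportive table. A cohort that recovers normally could appear to have a lingering raised temperature. If recovery speed differs between the age groups, the selection would also differ between the table's columns. The documents give no basis for saying whether it does.

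**Working it through.** The plan states no figure on this point, so there is nothing to reproduce. The check has two parts.

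**1. Who can have a reading under version A.** Let T be the hours from dosing to the start of the sustained normal run, and count visit hours as (day − 1) × 24. Day 3 is then 48 h, Day 7 is 144 h and Day 14 is 312 h. Recording ends at T + 48, so a subject still records at visit hour h only if T > h − 48.

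- Day 3: T > 0. Every subject febrile at entry still records.
- Day 7: T > 96 h.
- Day 14: T > 264 h.

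With S(t) = P(T > t), the share still recording is S(h − 48), the share of all subjects still febrile is S(h), and the febrile share among recorders is S(h) / S(h − 48). This last ratio is at least as large as S(h), whatever the distribution. The direction therefore needs no assumption about fever duration, only that the stop rule was followed.

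**2. An illustration of size at Day 7.** The documents give no distribution for T. Assume a log-normal with sigma 0.7 and every subject febrile at dosing, so S(t) = 1 − Φ(ln(t / median) / 0.7).

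| Assumed median T | Febrile, all subjects: S(144) | Still recording: S(96) | Febrile among recorders |
|---|---|---|---|
| 24 h | 1 − Φ(2.560) = 0.5% | 1 − Φ(1.980) = 2.4% | 22% |
| 36 h | 1 − Φ(1.980) = 2.4% | 1 − Φ(1.401) = 8.1% | 30% |
| 48 h | 1 − Φ(1.569) = 5.8% | 1 − Φ(0.990) = 16.1% | 36% |

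A simulation of 200,000 subjects per scenario gave 20.8, 29.7 and 36.6% for the last column, which agrees to within about one percentage point.

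To put this in degrees, assume a mean of 38.0 °C while febrile and 36.8 °C once normal, a gap of 1.2 °C. At a median of 36 h the all-subject Day 7 mean is 36.8 + 1.2 × 0.024 = 36.83 °C. Among recorders it is 36.8 + 1.2 × 0.296 = 37.15 °C. If all 120 planned subjects counted, about 0.081 × 120 = 10 would supply the Day 7 row. The infected population will be no larger than that.

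**Day 14.** Under the same assumptions S(264) is below 1% at all three medians, which is fewer than one subject in 120. The row would be almost empty.

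**Sensitivity to the distribution.** With an exponential T and a 48 h median, 12.5% of all subjects are febrile at Day 7 against 50% of recorders. With a Weibull of shape 1.5 and a 36 h median, the figures are 0.4% and 8%. The direction is the same and the size varies widely.

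**Sensitivity to the stop rule.** The documents also express the 48 h as four measurements. If the fourth 12-hourly reading ends recording, the stop comes 36 h after the first normal one. Some subjects then stop before Day 3: under Weibull durations with shape 1.0 or 1.5 and medians of 24 to 72 h, 71 to 95% still record there.

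**Under version B** every subject who keeps the diary contributes at every visit, and this selection does not arise.

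**The case against.** Several points on the other side stand.

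- **The effect is conditional.** A reader might infer that the table will certainly overstate late temperature. The documents do not support that, because Protocol 10.2.1 removes the stop. Version A is repeated in more places, including the training given to subjects, but repetition does not establish what was done.
- **The table is supportive.** SAP 5.2.1 lists time to resolution of fever as an endpoint, not temperature by visit. A reader might infer that the fever endpoint is biased too. It is essentially unaffected: resolution normally occurs before the stop rule is met, so the event is already in the diary. No hypothesis is tested, and the primary endpoint is safety.
- **The shrinking n will be visible.** SAP 8 requires the number contributing to be shown, and individual temperatures are listed in Listing 16.2.6.3. This discloses the selection but does not correct the mean.
- **The layout is not final.** The title of Table 14.2.1.1 does not mention study visit, and SAP 5 allows summaries by study day or time. Rows by study day would carry the same selection once subjects begin to stop.
- **The model is simplified.** It starts everyone febrile. Inclusion criterion 2a does not require fever, and SAP 5.1 plans to count subjects with a normal or low baseline temperature. Such subjects could stop around Day 3.
- **Clinic readings are not an unbiased substitute.** The antipyretic-timing control is written for subject-recorded temperatures. Protocol 10.1.2.3 to 10.1.2.5 state none for clinic readings, and only attendees contribute. They avoid selection by the stop rule and no more than that.

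A reader might also suppose that sites applied different rules, or that the bias differs by age group. Both are possible, but the documents show neither.

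**Conclusion.** The point holds in conditional form. If the 48-hour stop rule was applied, the Day 7 and Day 14 diary summaries are restricted by outcome and would overstate late temperature and the persistence of fever. Day 3 is largely unaffected for subjects febrile at entry. If Protocol 10.2.1 was followed, there is no such selection.

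The contradiction between the recording rules is a matter of text and holds without any assumption. The direction of the bias rests only on the stop rule. Its size (at Day 7 about 0.5 to 6% febrile among all subjects, against about 22 to 36% among recorders) rests wholly on an assumed log-normal duration, with sigma 0.7 and a median of 24 to 48 h, and on every subject starting febrile. It is an illustration and not a forecast. The matter is worth correcting because the remedy is cheap. It does not threaten the fever endpoint or the safety conclusions.

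**What to change.** 1. Reconcile Protocol 10.2.1 with the synopsis, 10.1, 10.1.2.2, Table 1 footnote 3 and SAP 1.1 and 1.2, and state in the SAP and the study report which recording rule was applied.
2. In Table 14.2.1.1, show at each visit the number recording, the number who stopped under the 48-hour rule, and the number missing for any other reason. Report percent febrile on the full infected-population (ITTI) denominator with rule-based stoppers counted as afebrile, and footnote that this assumes no relapse after stopping.
3. Add a summary of clinic-measured oral temperature at Days 3, 7 and 14 beside the diary summary. Footnote that antipyretic timing is not controlled at those readings and that only attendees contribute.
4. Rely on the Kaplan-Meier analysis for the time course of fever.

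The cost is a wording correction and a little extra tabulation for one supportive table. No new data collection is needed.
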